1.2. Schema

Table 1. Study Design

~360 Healthy adults ≥60 years of age randomized 2:1	Visit 1 (Day 1) Vaccination	Visit 2 1-Week Follow-Up Telephone Call 7-13 Days After Vaccination	Visit 3 1-Month Follow-Up Blood Draw 28-35 Days After Vaccination	Visit 4 2-Month Follow-Up Telephone Call 56-70 Days After Vaccination
Study Groups				
Group 1 RSVpreF n = 240	 			
Group 2 Placebo n = 120	 			
Safety				
Local reactions and systemic events ^a	Days 1 to 7 after vaccination			
AEs	Informed consent to Month 1			
AESIs SAEs NDCMCs	Informed consent to Month 2			
 Immunogenicity blood draw  Study intervention administration  Telephone contact for safety data				

a. Collected for 7 days, or longer for ongoing symptoms, after study intervention until symptom resolution.

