Review reactogenicity e-diary data	X	X				E-diary data are transmitted daily to a Web-based portal for review by the investigator or delegate (preferably on a daily basis) during the 7-day e-diary follow-up period. Assess and manage any noncompliance.
Ask the participant to contact site staff in the event of any severe local reactions or systemic events in the 7-day e-diary follow-up period	X					If the participant does not call, site staff must contact the participant to determine whether an unscheduled reactogenicity visit is required.
Remind the participant to bring their e-diary/smartphone to the next study visit	X	X				
Collect stop dates for any symptoms marked as ongoing on the last day of the e-diary collection period in the CRF		X	X	X		

Table 2. Schedule of Activities

Visit Number	Visit 1	Visit 2	Visit 3	Visit 4	Unscheduled Reactogenicity Visit	Notes
Visit Description	Day 1 Vaccination	1-Week Follow-Up	1-Month Follow-Up	2-Month Follow-Up	Safety Assessment	
Visit Window (Days)		7 to 13 Days After Vaccination	28 to 35 Days After Vaccination	56 to 70 Days After Vaccination	N/A	Day relative to study intervention administration (Day 1)
Type of Visit						 : Clinic visit,  : Phone visit
Ensure all e-diary data have been transferred, collect provisioned e-diary, or assist participant with deleting the application, as appropriate			X			Do not deactivate the e-diary until all data are confirmed as having been transferred to the e-diary data management system.
Obtain details and record any AEs	X	X	X		X	See Section 8.4.2 .
Obtain details and record any AESIs	X	X	X	X	X	See Section 8.4.8 .
Obtain details and record any SAEs and NDCMCs	X	X	X	X	X	See Section 8.4.2 .
Measure minimum and maximum diameter of redness (if present) or swelling (if present)					X	
If present, assess the severity of necrosis or exfoliative dermatitis at the injection site					X	
If present, assess the severity of any injection site pain					X	
If present, assess the severity of any systemic event (fatigue, headache, nausea, vomiting, diarrhea, muscle pain, or joint pain)					X	

PFIZER CONFIDENTIAL

CT02-GSOP Clinical Protocol Template Phase 1 2 3 4 (14 April 2023)

Table 2. Schedule of Activities

Visit Number	Visit 1	Visit 2	Visit 3	Visit 4	Unscheduled Reactogenicity Visit	Notes
Visit Description	Day 1 Vaccination	1-Week Follow-Up	1-Month Follow-Up	2-Month Follow-Up	Safety Assessment	

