8.3.4. Electronic Diary for Reactogenicity

Participants will be required to complete a reactogenicity e-diary through an application installed on a provisioned device or on the personal device of the participant. They will be asked to monitor and record prespecified local reactions, systemic events, and temperature daily for 7 days or longer following vaccination, where Day 1 is the day of vaccination. Participants will receive reminders to complete the reactogenicity e-diary on a daily basis, starting on the day of study intervention administration (Day 1) through Day 7, or longer if there are ongoing symptoms.

The e-diary allows recording of these assessments each day, thus providing an accurate representation of the participant's experience.

Data on local reactions, systemic events, and temperature recorded in the e-diary will be transferred electronically to the e-diary vendor, where they will be available for review by investigators, their qualified designees, and sponsor staff at all times via an internet-based portal. At intervals agreed to by the vendor and Pfizer, these data will be transferred

electronically to Pfizer for analysis and reporting. These data do not need to be recorded by the investigator in the CRF, except for the following conditions:

- Grade 4 local reactions will be collected in the CRF.
- Any local reactions or systemic events occurring within the first 30 minutes after study vaccination must be recorded on the CRF. The time of onset (relative to vaccination) must be recorded.
- If a participant withdraws because of prespecified event(s) recorded in the e-diary, the event(s) should be recorded on the CRF, regardless of whether the investigator considers the event(s) to be clinically significant.
- The investigator or designee must obtain stop dates for any symptoms ongoing on the last day, from Day 7 onwards until resolution. The stop dates should be documented in the source documents and the information entered in the CRF.

Investigators (or appropriately qualified designees) are required to review the e-diary data online at frequent intervals to evaluate participant compliance and as part of the ongoing safety review.

All provisioned e-diary devices must be collected per the study [SoA](#).

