8.10.2. Visit 2 (1-Week Follow-Up)

- Contact the participant by telephone.
- Review the participant's e-diary data and record the assessment in the CRF. Assess compliance, record any medically attended events (including hospitalizations), and collect stop dates of any symptoms ongoing on the last day of the e-diary collection period in the CRF. For symptoms still ongoing, continue to follow up until resolution and document and record stop dates in the CRF.
- Remind the participant to bring the e-diary to the next visit.
- Obtain details of any nonstudy vaccinations and prohibited medications and treatments as described in [Section 6.9.1](#).
- Record AE, NDCMCs, SAEs, and AESIs as described in [Section 8.4](#) and [Section 10.2](#).
- Remind participants to inform the study staff of any illnesses or medical events (eg, healthcare visits or hospitalization) that occur for the duration of the trial as described in [Section 8.3.4](#) and [Section 10.5](#).
- If appropriate, discuss contraceptive use as described in [Section 10.3.1](#).
- Complete the source documents.
- The investigator or an authorized designee completes the CRFs.

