The duration of each local reaction/systemic event will be calculated in days as the resolution date of reaction – start date of reaction + 1. Resolution of the event is the last day on which the event is recorded in the e-diary or collected in the CRF.

If there is no known end date, the duration will be considered unknown and set to "missing." Participants with no reported reaction have no duration.

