6.1.2.2. Supplementary Analysis

To support the assessment of reactogenicity, the endpoints below, as specified in [Section 3.1.2.1](#), will be summarized per the supplementary analysis with the same safety population:

- Duration (days) of each local reaction and each systemic event after vaccination.
- Onset day of each local reaction and each systemic event after vaccination.

The presentation of the results will include a basic descriptive summary without the 95% CIs for each vaccine group.

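### Setting duration to missing when no end date is known drops any reaction still ongoing at last contact from the supplementary duration summary, although its minimum duration is known

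*SAP*

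**What the plan says.** SAP 3.1.2.1, item 6, calculates duration in days as resolution date minus start date plus 1. Two sentences then decide what counts as an end:

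- The first defines when a reaction is over: "Resolution of the event is the last day on which the event is recorded in the e-diary or collected in the CRF".
- The second covers reactions for which this cannot be established: "If there is no known end date, the duration will be considered unknown and set to" missing.

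Item 6 has no censoring rule, no minimum duration and no count of unresolved reactions. SAP 5.3.1 refers missing safety data back to the endpoint sections, so item 6 governs.

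The result is used in SAP 6.1.2.2, which lists "Duration (days) of each local reaction and each systemic event after vaccination" as a supplementary analysis, presented descriptively by group without confidence intervals. SAP 5.2.2 sets the statistics for continuous variables: n, mean, median, SD, minimum and maximum. The standard listings named in SAP 6.6.1 are open-ended but do not mention unresolved reactions.

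On data collection, the protocol is thorough. The footnote to the Schema (1.2) reads "Collected for 7 days, or longer for ongoing symptoms, after study intervention until symptom resolution". Section 8.3.4 adds: "The investigator or designee must obtain stop dates for any symptoms ongoing on the last day, from Day 7 onwards until resolution". The Schedule of Activities (1.3) has this row marked for Visits 2, 3 and 4: "Collect stop dates for any symptoms marked as ongoing on the last day of the e-diary collection period in the CRF". Section 8.10.2 says: "For symptoms still ongoing, continue to follow up until resolution and document and record stop dates in the CRF".

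**The concern.** A reaction can lack an end date for different reasons. The date may never have been established, or the reaction may still have been present when the participant was last contacted. In the second case the duration is partly known: it is at least the time observed. That is a right-censored value. Setting it to missing discards the known minimum, and whether a value is discarded then depends on how long the reaction lasted.

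The sentence defining resolution raises a related problem. A participant whose diary stops while the symptom is present has a last recorded day. Read literally, that day becomes the resolution date and yields a short, apparently complete duration.

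At stake is the accuracy of one descriptive table in a study whose primary safety objective is to describe the safety profile. A reaction known to have lasted seven weeks or more would not appear in the table meant to show how long reactions last.

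**Working it through.** The plan gives no expected duration and no expected number of missing end dates, so there is no figure to reproduce. The check has four steps.

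**1. Which reactions can end up without an end date?** A reaction that outlasts Day 7 does not lack an end date for that reason. The diary is extended, stop dates are collected at Visits 2, 3 and 4, and item 6 accepts a CRF date as resolution. A reaction of 8, 20 or 45 days should therefore normally stay in the summary. That leaves three routes to a missing date: still ongoing at last contact, lost or withdrawn while symptomatic, or a date that could not be established.

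**2. Minimum duration if ongoing at Visit 4.** Inputs are onset on Day 1 to Day 7 (the reporting period in SAP 3.1.2.1) and Visit 4 at 56 to 70 days after vaccination (Protocol 1.3). Because Day 1 is the vaccination day, Visit 4 falls on Day 57 to Day 71. Using the SAP formula with the visit day in place of the resolution day:

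| Onset | Visit 4 on Day 57 | Visit 4 on Day 71 |
|---|---|---|
| Day 1 | 57 − 1 + 1 = 57 days | 71 − 1 + 1 = 71 days |
| Day 7 | 57 − 7 + 1 = 51 days | 71 − 7 + 1 = 65 days |

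Any such reaction has lasted at least 51 days.

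**3. Illustrative effect on the summary.** The RSVpreF group size of 240 comes from Protocol 9.5. The rest is assumed: 10%, 20% or 30% of the group report a given reaction (R = 24, 48 or 72), and known durations follow a geometric distribution with a mean of about 2.5 days. If k reactions are ongoing at Visit 4 and each is entered at 51 days, the mean is at least ((R − k) × 2.5 + k × 51) / R.

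| R | k = 1 | k = 2 |
|---|---|---|
| 24 | (23 × 2.5 + 51) / 24 = 4.5 | (22 × 2.5 + 102) / 24 = 6.5 |
| 48 | (47 × 2.5 + 51) / 48 = 3.5 | (46 × 2.5 + 102) / 48 = 4.5 |
| 72 | (71 × 2.5 + 51) / 72 = 3.2 | (70 × 2.5 + 102) / 72 = 3.8 |

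Under the current rule the reported mean would stay at about 2.5. The maximum would be 8 to 10 days instead of at least 51. The SD would omit a value 48.5 days from the mean (51 − 2.5). The median is 2 days either way.

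Two limits apply. If k = 0 there is no effect. If the date is missing for a reason unrelated to length, so that the dropped reaction is a typical one, the mean does not move.

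**4. The two sentences of item 6 applied to one record.** Suppose a symptom starts on Day 3, is entered on Days 3, 4 and 5, and the participant then stops reporting and is never reached.

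- Under the resolution sentence, the end is Day 5 and the duration is 5 − 3 + 1 = 3 days, as if resolved.
- Under the next sentence, no end date is known and the duration is missing.

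What is actually known is a duration of at least 3 days. Neither reading records that, and the SAP does not say which sentence applies.

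**The case against.** The strongest reply is that the protocol largely prevents the problem. Stop dates are mandatory and are pursued through Visit 4. Diary gaps are covered by the recall period in the e-diary and by investigator recall at the site visit (SAP 3.1.2.1 and 5.3.1). This stands, and it means that few reactions should be affected.

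A reader might infer that the rule removes the longest-lasting reactions in general, or that it can only shorten the reported durations. The documents support neither. Long reactions that resolve before Visit 4 should have a CRF stop date. A missing date can also belong to a short reaction, and dropping a below-average duration raises the reported mean. The downward direction is certain only for reactions already known to be long, as at Visit 4. For a participant lost early, the known minimum may be a few days.

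A reader might also infer that a persistent reaction vanishes from the safety results. It does not. It still counts in presence, maximum severity and onset (SAP 3.1.2.1, items 1 to 5). Where applicable, it also counts as medically attended, leading to withdrawal, or serious (SAP 3.3.3). The reported n would show a shortfall against the number with the reaction, though not the reason for it.

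Finally, the last-diary-day reading and the set-to-missing reading cannot both apply to one record. That is correct, and it is why this part is an ambiguity to resolve and not a second bias to add to the first.

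**Conclusion.** The point holds in a narrow form and is minor. Item 6 treats a reaction still ongoing at last contact as if nothing were known about its duration. If such a reaction is present at Visit 4 and no later stop date is obtained, a duration of at least 51 days is left out, and the mean, SD and maximum in the supplementary summary are understated. The median is essentially unaffected. The primary reactogenicity estimands are reporting rates and do not use duration; neither do the maximum-severity summaries.

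The 51-day minimum follows from the documents. The shifts in the mean and maximum rest on assumed reaction rates and durations, and the number of affected reactions cannot be derived and may be zero. The conflict between the two sentences of item 6 needs settling even if that number is very small, because two programmers could produce different tables from the same data.

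**What to change.** Change SAP 3.1.2.1, item 6, to state that:

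- a reaction not known to have resolved is censored at the last day it was known to be present, and is treated neither as missing nor as resolved;
- the same applies when diary entries stop while the symptom is present, so the last diary day counts as resolution only if the symptom is known to have ended.

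In SAP 6.1.2.2, for each group and reaction:

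- report the number ongoing at last contact, with their minimum durations listed, separately from the number whose end date is simply unknown;
- flag the maximum as a lower bound where an ongoing reaction makes it so.

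A Kaplan-Meier median is optional, worth adding only if more than a few reactions are censored; at small fractions it would add little to the median already planned.

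The cost is SAP wording and slightly more programming. No new data are needed, because the diary entries and the stop-date reviews at Visits 2, 3 and 4 are already planned.

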3.1.2.2. Adverse Events and Serious Adverse Events

Standard algorithms for handling missing AE dates and missing AE severity levels will be applied as described in the Pfizer vaccine data standard rules. Completely missing AE start dates will not be imputed.

The following derivations (yes/no) will be included for each participant:

1. Any AE reported through 1 month after vaccination: If the AE started on the same day of vaccination, and the AE start time is before the vaccination time, then this AE will not be counted. Otherwise, if the AE start time is missing or after the vaccination time, the AE will be included.
2. Any related AE reported through 1 month after vaccination: This is similar to the above except only the related AE is included.
3. Any immediate AE (AE start time is within 30 minutes after vaccination) reported after vaccination: This includes only AEs that started on the same day of vaccination and with a nonmissing AE start time that is within 30 minutes after vaccination.
4. Any severe or life-threatening AE reported through 1 month after vaccination.
5. Any AE leading to study withdrawal after vaccination.
6. Any AE leading to death after vaccination.
7. Any SAE reported throughout the study.
8. Any NDCMC reported throughout the study.
9. Any AESI reported throughout the study.

3.2. Secondary Endpoint(s)

RSV seroresponse 1 month after vaccination will be defined for each participant for subgroup A and subgroup B, respectively:

- If prevaccination results are \geq LLOQ, seroresponse is achieved if there is a ≥ 4 -fold rise from prevaccination results.
- If prevaccination results are $<$ LLOQ, seroresponse is achieved if the postvaccination titer is $\geq 4 \times$ LLOQ.

3.3. Other Safety Endpoint(s)

3.3.1. Adverse Events

AEs are classified into 1 of 3 tiers. Different analyses will be performed for different tiers (refer to [Section 6.3.1](#)).

- Tier 1 events: These are prespecified events of clinical importance and are maintained in a list in the product's safety review plan.

Guillain-Barré syndrome (from Day 1 through Day 43 after vaccination, where Day 1 is the vaccination day), atrial fibrillation (from Day 1 through the 1-month follow-up visit), and polyneuropathy (from Day 1 through Day 43 after vaccination, where Day 1 is the day of vaccination) have been identified as Tier 1 events for RSVpreF among the age group intended for this study. The RSV program Tier 1 list of MedDRA PTs is maintained by the safety risk lead in the CAETeLiSt and is referenced in the safety surveillance review plan for the program. The current list of Tier 1 events referenced by this study for RSVpreF should be confirmed to ensure that appropriate Tier 1 events will be used to produce final tables/graphs before conducting an analysis.

- Tier 2 events: These are events that are not Tier 1 but are “relatively common.” A MedDRA PT is defined as a Tier 2 event if at least 4 participants in at least 1 vaccine group report the event.
- Tier 3 events: These are events that are neither Tier 1 nor Tier 2 events.

3.3.2. Vital Sign Data

The temperature collected before the vaccination will only be used to assess any potential protocol deviation for vaccination temporary delay. Therefore, these will not be included as a baseline variable.

3.3.3. Additional Reactogenicity-Related Endpoints Collected From the CRF

Sites are expected to review the e-diary data on a daily basis. For any participants who experienced any reactogenicity during the e-diary collection period (Day 1 through Day 7), this reactogenicity will be further assessed to determine if it is immediate (within 30 minutes after vaccination); it causes any discontinuation from the study; it triggers medical attention, or it is an SAE. Therefore, additional endpoints based on these data collected from the CRF are derived as below.

- Immediate reactogenicity event.
- Reactogenicity event leading to withdrawal from the study.
- Medically attended reactogenicity event.
- Reactogenicity qualified as an SAE.
- Immediate event (including both immediate reactogenicity events and immediate AEs).

3.4. Other Endpoint(s)

Not applicable.

3.5. Baseline Variables

3.5.1. Baseline Definition

Day 1 is defined as the day of vaccination. Measurements or samples collected prior to vaccination on Day 1 are considered the baseline data for the assessments.

3.5.2. Demographics, Baseline, and Medical History

The demographic variables that will be collected include sex, race, ethnicity, tobacco use, and age at vaccination.

Medical history of clinical significance will be collected and categorized according to the current version (at the time of reporting) of MedDRA.

Tobacco use and prespecified existing medical conditions are collected at baseline and are categorized as the following groups of pre-existing medical conditions/tobacco use:

- Heart disease (including CHF and other heart disease);
- Lung disease (including COPD and other lung disease);
- Asthma;
- Diabetes mellitus;
- Liver disease;
- Renal disease;
- Current tobacco use (excluding past tobacco use).

3.5.3. E-Diary Completion

An e-diary will be considered transmitted if any data for the local reactions and systemic events are present for any day. If all data are missing for all items (local reactions and systemic events) in the e-diary for all 7 days after vaccination, then the e-diary will be considered not transmitted. An e-diary will be considered transmitted for a given day if any data are present for that day.

As the enhanced e-diary allows a recalling period for participants to enter missed responses in the e-diary, the following variables will be derived:

- E-diary data transmitted on each day of Day 1 through Day 7 within 24 hours of the e-diary reporting day.
- E-diary data transmitted on any day of Day 1 through Day 7 within 24 hours of the e-diary reporting day.

- E-diary data transmitted on each day of Day 1 through Day 7 regardless of the e-diary reporting day.
- E-diary data transmitted on any day of Day 1 through Day 7 regardless of the e-diary reporting day.

3.5.4. Nonstudy Vaccines

Any nonstudy vaccinations received from 28 days prior to study intervention administration through the conclusion of study participation will be collected.

Nonstudy vaccinations will be categorized according to the latest version (at the time of reporting) of the WHODD.

4. ANALYSIS SETS (POPULATIONS FOR ANALYSIS)

Data for all participants will be assessed to determine if participants meet the criteria for inclusion in each analysis population prior to unblinding and releasing the database and classifications will be documented per standard operating procedures.

For purposes of analysis, the following analysis sets are defined:

Participant Analysis Set	Description
Screened population	All participants who have a signed ICD in the study.
Randomized population	All screened participants who are assigned a randomization number in the IRT system in this study.
Safety population	All screened participants who receive the study intervention in the study.

Defined Analysis Set	Description
Evaluable immunogenicity population	
All participants who meet the following criteria:
 
 • Are eligible for the study; • Receive the study intervention to which they were randomized; • Have the 1-month postvaccination blood collection visit within 27-42 days after vaccination; • Have at least 1 valid and determinate assay result 1 month after vaccination; • Have no major protocol violations from vaccination through the 1-month postvaccination blood draw.

Defined Analysis Set	Description
miITT immunogenicity population	All participants who were randomized and had at least 1 valid and determinate assay result after receiving the study intervention.

